**1. Determine the efficacy of an adaptive progressive VI reinforcement intervention for reducing cocaine use in the short- and long-term.** The hypothesis is that patients assigned to the adaptive progressive VI reinforcement intervention will achieve longer periods of abstinence than patients in standard care during the period reinforcement is in effect (24 weeks). We will also evaluate how well this reinforcement intervention maintains benefits throughout follow-up (18 months).

**2. Compare the relative efficacy of adaptive progressive VI reinforcement to a traditional reinforcement intervention.** Patients receiving adaptive progressive VI reinforcement are hypothesized to achieve greater during and post-treatment abstinence than those receiving traditional twice-weekly reinforcement.

Secondary and exploratory aims of the study are to:

**a. Evaluate relations between behavioral and measures of cognitive control and response to monetary rewards and treatment outcomes.** Patients with better cognitive control are expected to achieve longer durations of abstinence, regardless of treatment assignment. Patients who are more sensitive to monetary rewards are expected to achieve longer duration of abstinence, particularly when assigned to a reinforcement intervention. We also expect that sensitivity to monetary rewards and cognitive control may increase among those who are assigned to a reinforcement intervention, and that changes in these processes may mediate drug use outcomes.

**b. Assess the impact of reinforcement interventions on HIV risk and other outcomes.** Compared to SC, reinforcement interventions are expected to reduce high risk sexual behaviors that spread infectious diseases. Reinforcement interventions are also hypothesized to decrease psychiatric symptoms and improve quality of life. Both short-term and long-term effects will be examined. Gender effects will also be explored.

**c. Estimate costs and cost-effectiveness.** We will examine costs and cost-effectiveness of interventions and estimate conditions under which, and patients for whom, these interventions may be most cost-effective.

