**Data Analysis.** An important issue preceding analyses is to identify baseline differences between groups despite random assignment. Differences between groups that may be related to outcome (e.g., psychiatric diagnoses, dependence severity, clinic services received) will be used as covariates or fixed factors, as appropriate. Analysis will be conducted on an intent-to-treat basis, using all randomized patients, and both short-term (changes from baseline to month 6) and longer-term (throughout the 18-month follow-up) efficacy will be evaluated. The primary outcome is longest duration of cocaine abstinence, a continuous variable that can be transformed if needed. Groups will be compared using t-tests for normally distributed data, or ANCOVA if covariates are included. The design includes 3 treatment groups, allowing for analyses of two main effects.

Primary aim # 1 is to examine the efficacy of adaptive progressive VI reinforcement. We will compare those randomized to Group C vs Group A with respect to longest duration of abstinence during the 24-week intervention period and throughout the 18-month follow-up period.

Primary aim #2 is to assess if adaptive reinforcement improves duration of abstinence achieved relative to traditional reinforcement. We will compare those randomized to the two reinforcement conditions with respect to during treatment and long-term abstinence outcomes.

Secondary aims are to evaluate the impact of the interventions on other indices of stimulant and secondary drug use outcomes. Using the same contrasts above, we will compare groups with respect to: proportions of submitted and expected samples that test negative for stimulants and other drugs (alcohol, opioids, THC), and subjective reports of use (SUC % abstinent days). The first rely on objective indicators and such data will be available from all randomized patients. Subjective reports will supplement objective indices, and patients can be considered using if either index is positive. In terms of proportional data, missing samples will be considered missing (not impacting the denominator) in one analysis, and positive in another to consider the range of possibilities with respect to drug use outcomes. Because Group B has more expected samples (48) than the other groups ( $\geq 18$ ), proportional data for expected samples will rely upon the cell phone prompted samples ( $\geq 18$ ), designed to be similar across conditions, to conservatively test group differences.

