**Power analyses for primary aims.** Our studies reinforcing abstinence generally find Cohen's  $d$  effect sizes of 0.6 to  $> 1.0$  for during treatment drug use outcomes (Petry et al, 2000, 2002,2004,2005abc,2006a, 2007a,2010b,2011a,2012abc). In terms of post-treatment effects, our ongoing study is finding an effect size of 0.46 for a 12-week reinforcement intervention in enhancing post-treatment abstinence relative to standard care. Although we expect a larger effect size when 24 weeks of reinforcement is provided, and especially if more patients engage in the adaptive progressive VI reinforcement intervention for greater durations, we will conservatively power this study to detect a similar effect size of 0.46 between the VI reinforcement intervention and standard care for long-term outcomes. Using a Type I error rate of  $\alpha=.05$ , a Type II error rate of  $\beta=.20$ , and power=0.80 (Cohen, 1988), 60 patients/ group are needed to detect  $d=0.46$  between the standard care and reinforcement interventions (Aim 1). For Aim 2, the study is powered to detect a lower, but still clinically meaningful, effect size of 0.35 between the two active reinforcement conditions, similar to effect sizes found between reinforcement conditions in other studies (Petry et al., 2004, 2006a). Using the same power analyses outlined above, 110 patients/group are needed to detect  $d \geq .35$  between the traditional and adaptive reinforcement conditions with respect to during treatment and long-term outcomes. Thus, we will recruit 280 patients (60 in standard care and 110 each for the reinforcement interventions).

**Secondary aims** are to evaluate if reinforcement improves other indices of drug use, psychosocial functioning (ASI, BSI scores), quality of life, and HIV risk behaviors, as found in other studies (Ghitza et al., 2008; Hanson et al, 2008; Petry et al., 2007b,in press b). These are continuous measures, with missing data likely. If no systematic differences in missing data are noted (the case in our prior studies), hierarchical linear models (HLM; Gibbons et al., 1993) using MIXREG (Hedeker, 1993) will analyze differences between groups over time. These analyses have advantages over repeated measures ANOVA as they estimate missing data via model parameter

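### Sidedness of the primary tests is not stated, and the sample sizes do not fit a two-sided 5% t-test: on that reading Aim 2 has 73% power, not 80%

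*Combined protocol and SAP*

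**What the plan says.** Under Power analyses for primary aims, the plan takes a Type I error rate of .05 and a Type II error rate of .20. For adaptive reinforcement against standard care (Aim 1) it states "and power=0.80 (Cohen, 1988), 60 patients/ group are needed to detect" d = 0.46. For adaptive against traditional reinforcement (Aim 2) it states "Using the same power analyses outlined above, 110 patients/group are needed to detect" an effect of at least 0.35, for both during-treatment and long-term outcomes. The total follows from these two figures: "Thus, we will recruit 280 patients (60 in standard care and 110 each for the reinforcement interventions".

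The Data Analysis section names the primary test: "Groups will be compared using t-tests for normally distributed data, or ANCOVA if covariates are included". Analysis is by intention to treat, on all randomized patients.

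The hypotheses under Specific aims are directional. For Aim 2: "Patients receiving adaptive progressive VI reinforcement are hypothesized to achieve greater during and post-treatment abstinence than those receiving traditional twice-weekly reinforcement". Nowhere does the plan call a primary test, or the power calculation, one-sided or two-sided.

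**The concern.** Two sample sizes said to come from the same calculation should both follow from one set of inputs. These do not, and the missing input is the sidedness of the test.

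The gap matters most for Aim 2, a primary aim whose two arms hold 220 of the 280 patients. A null result for adaptive against traditional reinforcement would be read against a stated 20% risk of missing d = 0.35. If the true risk is nearer 27%, that result says less than the plan implies.

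The rejection rule is also left open. A difference in the predicted direction with a two-sided p between .05 and .10 would be significant on one reading and not on the other.

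**Working it through.** **Inputs, all from the power and Data Analysis sections.** Alpha .05 (sidedness not given); power 0.80; d = 0.46 with 60 per group (Aim 1); d = 0.35 with 110 per group (Aim 2); allocation 60 : 110 : 110; two-sample t-test. The power section contains no allowance for dropout or multiplicity.

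**Formulas.** With d standardised (SD = 1), the noncentrality is λ = d·√[n₁n₂/(n₁+n₂)] on n₁+n₂−2 degrees of freedom. Power is the probability that a noncentral t exceeds the critical value. As a hand check, n per group ≈ 2(z_α + z_β)²/d², with z_β = 0.842 and z_α = 1.960 (two-sided) or 1.645 (one-sided).

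**Step 1. Reproduce the plan's sample sizes (80% power).**

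| | Stated | Two-sided: hand formula | Two-sided: exact t | One-sided: hand formula | One-sided: exact t |
|---|---|---|---|---|---|
| Aim 1, d = 0.46 | 60 | 2(2.802)²/0.2116 → 75 | 75.2 → 76 | 2(2.487)²/0.2116 → 59 | 59.1 → 60 |
| Aim 2, d = 0.35 | 110 | 2(2.802)²/0.1225 → 129 | 129.1 → 130 | 2(2.487)²/0.1225 → 101 | 101.6 → 102 |

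The 60 reproduces one-sided only. The 110 reproduces neither way.

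**Step 2. A check that does not depend on sidedness.** Required n scales with 1/d². If 60 is right for 0.46, the same method gives 60 × (0.46/0.35)² = 60 × 1.727 ≈ 104 for 0.35. The stated 110 is larger, so the two figures are not exact requirements from one calculation.

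**Step 3. Power at the planned sizes, without covariates.**

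| Comparison | λ | Two-sided | One-sided |
|---|---|---|---|
| Aim 2, 110 v 110, d = 0.35 | 0.35 × √55 = 2.596 | 73.4% | 82.7% |
| Aim 1 as worded, 60 v 60, d = 0.46 | 0.46 × √30 = 2.520 | 70.5% | 80.5% |
| Aim 1 as recruited, 60 v 110, d = 0.46 | 0.46 × √38.82 = 2.866 | 81.3% | 88.7% |

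For Aim 2 the critical values on 218 df are 1.971 (two-sided) and 1.652 (one-sided). The normal approximation agrees: Φ(2.596 − 1.960) = 73.8% and Φ(2.596 − 1.645) = 82.9%.

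**Step 4. Effect detectable with 80% power at 110 v 110.** Two-sided d = 0.379; one-sided d = 0.336.

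**Step 5. What covariate adjustment could recover (assumption).** The plan gives no covariate–outcome correlation r. Taking the effective effect as d/√(1−r²), two-sided Aim 2 power is 75.1% at r = 0.2 (d = 0.357) and 80.5% at r = 0.4 (d = 0.382). It reaches 80% at r ≈ 0.39, where covariates explain about 15% of outcome variance.

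**The case against.** The strongest reply is that the plan was meant to be one-sided. Its hypotheses are directional, its 60 is exactly the one-sided requirement, and Aim 2 is said to use the same method. On that reading 110 is a surplus over 102 and the promised 80% is exceeded. The 110 could be 102 rounded up to the next ten, a step that leaves 60 unchanged. It could also be an allowance for about 8% loss (101/0.92 → 110), although the same allowance would take Aim 1 to 65 (59/0.92).

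This has weight. One-sided testing fits the numbers better than two-sided, and the shortfall is conditional on the two-sided reading. But a directional hypothesis is not a stated one-sided test, and the plan mentions neither rounding nor a loss allowance. If one-sided tests were intended, an analyst reading .05 in the usual way would run a test for which the trial was not sized. The case for stating sidedness is the same either way.

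A second reply is that ANCOVA restores the power. It might: the Randomization section calls the initial toxicology result a strong predictor of outcome. But the Data Analysis section brings in covariates only where groups differ at baseline, and the plan does not rely on adjustment for power or state a correlation.

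A third reply is that the shortfall is modest: detectable d moves from 0.35 to 0.38, and Aim 1 is unaffected. That is correct, and it is why a restatement is enough.

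**Conclusion.** The concern holds. Sidedness is unstated, and the Aim 2 sample size does not follow from the plan's own inputs under either convention. If the tests are two-sided, Aim 2 has 73% power at d = 0.35, about 7 percentage points below the stated 80%. If they are one-sided, it has 83%. Which applies cannot be settled from the documents.

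These figures assume a t-test without covariates, the full .05 for each aim, equal variances, and every randomized patient contributing an outcome. Aim 1 as recruited exceeds 80% on both readings, though the plan does not compute power for that 60 v 110 comparison.

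**What to change.** State in both the Data Analysis and power sections whether the primary tests are one- or two-sided. Settle and document the choice before any outcome is compared by group. Then restate power to match:

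- **If two-sided:** 81% for Aim 1 (60 v 110, d = 0.46) and 73% for Aim 2 (110 v 110, d = 0.35), with 80% reached at d = 0.38.
- **If one-sided at 5%:** say so, use that test in the analysis, and give 89% for Aim 1 (60 v 110) and 83% for Aim 2 (110 per group, 102 needed).

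If covariate adjustment is relied on for power, name the assumed correlation. Any long-term power after loss to follow-up should be marked as an illustration under a stated assumption. For example, if 94% per group were analysed, Aim 2 and Aim 1 would have about 71% and 79% two-sided, or 81% and 87% one-sided.

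The cost is wording only, with no change in enrolment. If the tests are two-sided, the one figure that becomes less favourable is the Aim 2 power.

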**A. Standard treatment (weeks 1-24):** Patients assigned to this condition will receive standard care, consisting of group therapy, including daily planning, 12-Step therapy, relapse prevention, coping and life skills training, recreation training, focus groups for depression and anxiety, and AIDS education. Intensity starts at 3-4 groups

per day 3-5 days per week and is gradually reduced to 1 aftercare group per week. Individual and family counseling is provided on an as-needed basis, usually only for crises. Groups are led by recovering individuals, nurses, and MA level counselors. Format and intensity of care is similar across clinics.

Study patients will undergo regular urine and breath sample monitoring for 24 weeks. In the first three weeks, twice weekly testing will be arranged, coinciding with early and late weekdays of clinic attendance (M-Th, M-F, Tu-Fri). Thereafter, days selected for sample collection will be randomly selected from patients' twice weekly preferred schedule (M-Th, M-F, or T-F), which may or may not coincide with group therapy, as some patients will have ceased attending groups. RAs will phone or text (patient's preference) on the morning of each testing day to inform them whether or not to leave a sample that day. For example, in weeks 4-9, a patient with a M-F schedule may be asked to come in on Mon, Mon, Fri, Mon, Fri, Mon in the respective weeks. Patients will be told to plan to leave a sample on each of their test days, and will be phoned or texted on average every other possible test day in weeks 4-9 and told they need not leave a sample that day. In weeks 10-24, days for sample collection will reduce to once every 2-3 weeks on average. Patients need only avail themselves for sample collection on two days per week (beginning and end of each week), and the schedule of availability can change over the 24-week period (e.g., from M-Th to T-F) so long as patients give at least one week notice. Patients will receive \$2 per requested sample submitted, plus a \$20 bonus if they submit all requested samples in a four week period (regardless of results). In the case of an excused absence, patients can come in the next day to submit a sample and still be eligible for the \$20 bonus.

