with sample collection days occurring at the beginning and end of the week and coinciding with regular clinic attendance (when applicable) and patient preference for days (M-Th, M-F, or T-F). Once patients in this group achieve ~3 weeks of continuous abstinence, they will be expected to submit samples on average once a week for the next 6 weeks (phase 2). After 9 full weeks of abstinence, sample collection will decrease to every other week on average for the next six weeks (phase 3), and finally patients who maintain abstinence will be transitioned to a testing and reinforcement schedule of every three weeks on average for the final 9 weeks of the 24-week treatment period (phase 4). In total, an average of  $\geq 18$  samples will be scheduled over 24 weeks in patients maintaining abstinence. As in Groups A and B, patients will receive \$2 per requested sample submitted, plus a \$20 bonus if they submit all requested samples in a four week period (regardless of results). In the case of an excused absence, patients can come in the next day to submit a sample and still be eligible for the \$20 bonus.

As in Group B, patients earn 1 draw per negative sample, and draws earned increase by one draw for consecutive negative samples during the twice-weekly testing phase (phase 1). To accommodate for the reduced overall number of samples submitted relative to Group B and to maintain overall equal maximum reinforcement between conditions, once a patient moves to the phase 2 sample schedule (once a week) draws per negative sample increase by 2 draws for each consecutive negative sample provided. Draws continue to increase by 2 up to a cap of 25 draws per negative sample, which would be achieved after about 15 weeks of abstinence.

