To determine if patient factors predict outcome, multiple regression analyses will be used to find predictors of continuous measures (e.g., longest duration of abstinence, percent negative samples), and logistic regressions for dichotomous dependent variables (e.g., presence or absence of stimulant use at follow-up). Cox regression analyses may also be used to determine what factors predict time to event outcomes, such as time to first positive sample after study initiation. Independent variables will include treatment condition, site, days attended groups at the clinic, drug use severity (ASI-drug scores, baseline positive samples), scores on cognitive control tasks at baseline (computer task or impulsivity scores), and demographics, including gender and race. Analyses will be conducted for the entire sample and with interactions of predictors with condition to assess if certain characteristics are more predictive of outcomes in the different treatment conditions.

Behavioral changes that result from treatment may also be a function of improving cognitive control, and reinforcement interventions may lead to reductions in drug use by enhancing cognitive functioning. If effects of reinforcement on drug use outcomes are significant, cognitive control as assessed via computer and impulsivity tasks will be evaluated as a potential mediator of effects. A latent growth model using structural equation modeling can be built. Models will be built sequentially, starting with a basic latent growth model comprising drug use days over time, modeled as slope and intercept. Important cognitive performance indices can be tested as mediators in turn. A bootstrapping resampling procedure will estimate model test statistic  $p$  values and parameter standard errors (Arbuckle, 2006). Models will be considered to fit the data if the chi-square is not significant, Comparative Fit Index (CFI) is  $>.97$ , and root mean square error of approximation (RMSEA) is  $<.10$  (Bollen & Long, 1993) using an iterative basis, with individual paths added or deleted on the basis of modification indices (Jöreskog & Sörbom, 1984). Once a basic latent growth model is determined, treatment group will be added as a predictor of slope and intercept. Then, cognitive variables (pre to post change scores) included in the model. Beta weights of the full model can be tested using a product of coefficients test to determine if mediation is significant (MacKinnon 2007a,b).

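### If the optional Cox model for time to first positive sample counts every urine sample, Group B's denser schedule can create a false difference from Group C; the prompted-sample rule should cover this endpoint

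*Combined protocol and SAP*

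**What the plan says.** In the combined protocol and SAP, the Data Analysis paragraph on patient factors that predict outcome offers Cox regression, as an option, to find predictors of "time to event outcomes, such as time to first positive sample after study initiation". The covariates follow: "Independent variables will include treatment condition, site, days attended groups at the clinic", and others. Interactions of predictors with condition are also planned. The paragraph does not say which samples count, and it does not mention interval censoring.

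The testing schedules are set out by arm under Methods:

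- **Group A:** "In the first three weeks, twice weekly testing will be arranged". Patients then "will be phoned or texted on average every other possible test day in weeks 4-9" to say that no sample is needed. Finally, "In weeks 10-24, days for sample collection will reduce to once every 2-3 weeks on average".
- **Group C:** twice weekly until about three weeks of abstinence, then weekly on average for six weeks, every other week for six weeks, and every three weeks for the last nine. Each step down requires continued abstinence.
- **Group B:** a twice-weekly reinforced schedule for all 24 weeks, 48 samples in total. Phone prompts run only at the frequency used in Groups A and C, so most of the schedule after week 3 is unprompted.

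Earlier in Data Analysis, under the secondary drug-use outcomes, the plan acknowledges 48 expected samples in Group B against at least 18 elsewhere. It limits the expected-sample proportions to phone-prompted samples. That rule is stated for proportional data only. The Group B section says that relapse indicators will be comparable across groups and points to the analyses, but the analysis text does not extend this to time to first positive sample.

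**The concern.** A first positive can be dated only on a day when a sample is given. If one arm gives more samples than another, the same pattern of use is found sooner and more often in that arm. A standard Cox model takes the sample date as the event date and has no term for how often patients were tested, so the difference in detection appears as an effect of condition.

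The B v C contrast is the exposed one. A spurious excess of early positives in Group B would favour the adaptive arm, which is the direction hypothesised in primary Aim 2. A reader could take it as support for that aim. The predictor-by-condition interactions would carry the same artefact.

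**Working it through.** **Step 1: reproduce the plan's sample counts.**

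- Group C, abstinent throughout: 3×2 + 6×1 + 6/2 + 9/3 = 6 + 6 + 3 + 3 = 18.
- Group A: 3×2 + 6×1 + 15/3 = 17, up to 3×2 + 6×1 + 15/2 = 19.5.
- Group B: 24×2 = 48.

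These match the plan's 48 and at least 18. All arms have 6 scheduled samples in weeks 1-3. In weeks 4-24, Group B has 21×2 = 42 and Group C has 6 + 3 + 3 = 12. In weeks 10-24, the counts are 15×2 = 30 and 3 + 3 = 6.

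**Step 2: direction.** If use is identical and the extra samples are given regardless of recent use, they can only bring a first positive forward or add one. They cannot delay one.

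**Step 3: size, by simulation with identical use in both arms.**

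- *From the documents:* two possible test days a week; Group C tested on each with probability 1, 1/2, 1/4 and 1/6 in weeks 1-3, 4-9, 10-15 and 16-24; 10 use days a month (Design considerations); 110 patients per reinforcement arm (Power analyses).
- *Assumed:* a detection window of 2, 3 or 4 days; the shape of the use process; the share of Group B's unprompted samples that is given.
- *Method:* Cox model with arm as the only covariate. Hazard ratios come from 20,000 patients per arm. False-positive rates come from 300 trials of 110 per arm at two-sided 0.05.

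Null hazard ratio, B v C (range over the three windows), by share of unprompted samples given:

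| Use, identical in both arms | All | Half | Quarter | None |
|---|---|---|---|---|
| Sporadic, averaging 1 day/month | 1.42-1.64 | 1.28-1.38 | 1.14-1.20 | 1.00-1.01 |
| Sporadic, averaging 0.5 day/month | 1.65-1.90 | 1.40-1.51 | 1.21-1.30 | 0.99-1.02 |
| Relapse (median onset 12 weeks), then 10 days/month | 1.17-1.23 | 1.12-1.20 | 1.09-1.13 | 0.98-1.01 |
| Mixed, averaging 10 days/month from the start | 1.09-1.16 | 1.08-1.09 | 1.03-1.06 | 1.00-1.03 |

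With full submission, the false-positive rates for the four rows are 63-83%, 84-92%, 18-26% and 8-9%. With half submission they are 31-48%, 44-52%, 13-16% and 2-5%. With prompted samples only, they are 0-7%.

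Relapse onset taken instead as exponential with mean 20 weeks gave about 1.1-1.3 at 10 days a month. As an example from the first row, with a 3-day window and full submission, the median first positive is day 35 in Group B and day 56 in Group C, and 83% v 63% are ever positive.

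**Step 4: A v C.** With a 3-day window, the null hazard ratio is 0.98-1.01 across the four patterns.

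**Step 5: submission that depends on use.** If patients in Group B skip unprompted days after using, the unprompted samples are never positive and the first positive again comes only from prompted ones. Simulated hazard ratios under that behaviour were 0.92-1.06.

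**The case against.** The other side has several good points.

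- **The analysis is optional and exploratory.** The plan says that Cox regression may be used, and time to first positive is only an example. Arms are compared on longest duration of abstinence and by the mixed-model contrasts. A reader might infer that this hazard ratio is a planned test of an aim; the text does not support that.
- **Full submission by Group B is unlikely.** The protocol expects a median clinic stay under 5 weeks, and only 33% completed 12 weeks in the longest reinforcement arm of the sponsor's ongoing trial. This reduces the bias but need not remove it: unprompted negatives earn prize draws and a missed sample resets them, so engaged patients have reason to give them.
- **The sign is not guaranteed.** A reader might infer that Group B must look worse. In Group B, a missed and a positive sample both reset the draws, and the $2 is paid for requested samples, so a patient who has used gains little by bringing an unprompted one. Step 5 shows that the bias can then disappear.
- **The hazard is not use rate times testing rate.** That reading would give about 42/12 = 3.5 in weeks 4-24. At 10 use days a month almost any test finds use, and the simulated ratio is far smaller. Values of 2.3-3.0 arise only with one isolated day of use in 24 weeks, an extreme pattern.
- **The sponsor argues in Design considerations that use will be found at the next random test.** This does not answer the point: the next test is 3-4 days away in Group B and may be three weeks away in Group C.

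What remains is that, for this endpoint, nothing in the plan keeps Group B's unprompted samples out of the event.

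**Conclusion.** The concern holds in a limited form. As written, the optional Cox analysis can show Group B with earlier and more frequent first positives than Group C when use is the same. With full submission and a 2-4 day window, the null hazard ratio is about 1.1-1.3 at 10 use days a month after relapse and about 1.4-1.9 for sporadic use. It shrinks with partial unprompted submission and is about 1.0 if none is given or if it is skipped after use. It is also small when most first positives fall in weeks 1-3, where testing is equal (roughly 64-73% of patients in the mixed heavy-use pattern).

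The window, the submission share and the distribution of use between patients are assumptions that the documents do not settle, so the ranges are illustrative. A reader might also infer that both reinforcement contrasts with standard care are distorted. For A v C the documents point the other way: the two schedules are nearly the same, Group A's test days are adjusted to Group C's running average, and the simulated ratio is about 1.0. The primary outcome is not at issue here. This is a cheap improvement.

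**What to change.** In the Data Analysis paragraph on predictors, extend the existing rule: time to first positive sample is defined on phone-prompted samples only, in all three arms. The twice-weekly samples of weeks 1-3 should count as prompted everywhere, as the plan's figure of at least 18 already implies. This alone brings the null hazard ratio back to 0.98-1.03.

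Preferably, treat the event as interval-censored between the last negative and the first positive prompted sample, so that a missed prompt widens the interval.

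Two cautions:

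- An alternative event based on self-report or urine must also limit urine to prompted samples; otherwise the detection difference returns.
- Fixed calendar testing phases should not be used as a model term for Group C, because its phase depends on each patient's abstinence.

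The cost is a sentence or two of analysis text, with no change to trial conduct. Group B's unprompted samples are not used for this exploratory endpoint.
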